After providing study information, participants will be randomized to one of three unique message packages: (1) Message A (hope-based video message and flyer; n = 275), (2) Message B (fear-based video message and flyer; n = 275), or (3) Control Message C (water advertisement video and flyer; n = 275). These messages will be presented as part of a (~15 minute) online survey, conducted via Qualtrics (a secure, web-based application designed to support data capture for research studies) and collected by Centiment LLC. The survey will first assess demographic characteristics (i.e., age, race, ethnicity, gender identity, income level, education level), psychiatric history (i.e., self-report of current or lifetime psychiatric diagnosis), smoking history (e.g., cigarettes smoked per day, age of smoking onset) and current motivation to quit smoking. Participants will then view their randomized message package (A, B, or C), and will be asked to rate their emotional response to this message, and the impact of the presented messages on motivation to quit (only in Message A and B conditions) and behavior change mechanisms outlined in the HBM: perceived susceptibility, perceived severity, perceived benefits, perceived barriers, self-efficacy. Upon completion, participants will be paid for their time and effort by Centiment LLC, through secure PayPal payments. Per projections from Centiment, in order to recruit the planned 825 participants, participants will be compensated for their time and effort based on Centiment LLC's approved compensation strategy.

Eligibility Criteria

Eligibility criteria include self-identifying as African American or Black (can identify as AA along with other race), current smoker (defined as smoking >100 cigarettes in their lifetime and currently smoking cigarettes 'some days' or 'everyday'), able to read and write in English, ages 50-80, no self-reported history of MCI or dementia.

Recruitment

Participants selected for this study will be recruited to represent the national (U.S.) populations of older adults, particularly by gender (approximately 50 percent female ± 10 percent). Participants will be recruited via text message from a pre-existing pool of potential participants within the U.S. using a market research company (Centiment, LLC). Centiment is a large market research company with a pool of thousands of pre-existing individuals who are solicited to engage in various studies Centiment is

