contracted to support. The company has reach in over 100 countries with a vast array of background demographic information on potential participants including race, gender, age, medical history (self-reported), and behaviors (including smoking status as identified in the Participants section). Potentially eligible participants for this study from Centiment's pool of individuals (based on eligibility criteria described in the section above) will be sent an invitation via text message to complete the study survey, those who then respond and complete the survey will be considered enrolled in this study.

Statistical Analysis Plan

Data analysis will be performed using IBM SPSS Statistics. Chi-square tests of independent and Analyses of Variance (ANOVAs) will be used to confirm randomization resulted in no significant differences between groups in terms of demographics, smoking-related variables, and psychiatric history. ANCOVA tests with planned contrasts will be used for primary analyses. Primary analyses will control for baseline values (of motivation and intention to quit, respectively) due to the risk of bias of baseline variables. Secondary analyses will compare the messages to each other using ANOVAs to examine the effect of condition on perceived message effectiveness, reactance, and informativeness. Analyses of emotionality will use ANOVAs. Lastly, Benjamin-Hochberg corrections, which are less susceptible to type II error than other forms of statistical corrections, will control for false discovery rate (FDR) for covariate-corrected analyses involving emotionality.

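### Cheap improvement: the secondary comparison of messages could name A versus B as its target and adjust for two baseline measures the survey already collects

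*Combined protocol and SAP*

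**What the plan says.** The Statistical Analysis Plan section treats the two tiers of analysis differently.

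- **Primary:** "ANCOVA tests with planned contrasts will be used for primary analyses". The covariates are named: "Primary analyses will control for baseline values (of motivation and intention to quit, respectively").
- **Secondary:** "Secondary analyses will compare the messages to each other using ANOVAs to examine the effect of condition on perceived message effectiveness, reactance, and informativeness". No covariate or contrast is given.

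Under Study Procedures, "participants will be randomized to one of three unique message packages": a hope-based message (A), a fear-based message (B) and a water advertisement (C), with 275 people each. The survey opens with demographics and psychiatric history, then "smoking history (e.g., cigarettes smoked per day, age of smoking onset) and current motivation to quit smoking". Only after that is the message shown. Ratings of the message's impact on motivation to quit are limited to arms A and B. No such limit is stated for perceived effectiveness, reactance or informativeness.

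**The concern.** Two things are left on the table.

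**Precision.** Two baseline measures that might predict how a smoker rates a quit message are in the dataset for every arm, yet the secondary model uses neither. If they do predict the ratings, the A-versus-B comparison is less precise than it could be at the same cost.

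**Target.** The secondary analyses are meant to set the messages against each other, but the number of levels of *condition* is not stated. With A and B only, the F test is the A-versus-B test. With C as well, a significant F may show only that a water advertisement is rated differently from both quit messages. That would not tell the team whether the hope-based or the fear-based package did better.

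**Working it through.** **Inputs from the documents.** 275 per arm, three arms; 3 × 275 = 825, which matches the planned total. No alpha, power, effect size, SD or correlation is given, so 275 itself cannot be re-derived.

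**Assumptions.** Two-sided alpha 0.05; full data on 275 per arm; A–B difference d in SD units; r = multiple correlation of the two covariates with the rating within arm. I use d = 0.24 because it gives about 80% unadjusted power. It is not a target of the trial.

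**1. Gain from the covariates (A versus B).** Noncentral t, with noncentrality = d / √(1 − r²) × √(275/2). Error degrees of freedom are 550 − 2 = 548 unadjusted and 550 − 2 − 2 = 546 with two covariates.

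For d = 0.24 and r = 0 the noncentrality is 0.24 × 11.726 = 2.814. For r = 0.3 it is 2.814 / √0.91 = 2.950.

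| r | Power, d = 0.24 | Power, d = 0.20 | Difference detectable with 80% power (SD) |
|---|---|---|---|
| unadjusted | 80.2% | 64.8% | 0.239 |
| 0 (two useless covariates) | 80.2% | 64.8% | 0.239 |
| 0.1 | 80.6% | 65.3% | 0.238 |
| 0.2 | 81.8% | 66.6% | 0.235 |
| 0.3 | 83.8% | 68.9% | 0.228 |
| 0.5 | 90.0% | 77.1% | 0.207 |

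The two lost degrees of freedom cost nothing visible. At d = 0.24 the gain is 0.4 points at r = 0.1 and 1.6 at r = 0.2; it becomes useful from about r = 0.3.

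**2. What a three-arm F would show.** Noncentral F on 2 and 822 degrees of freedom, λ = 275 × Σ(arm mean − grand mean)², means in SD units.

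*A equals B, only C differs.* With a gap c, Σ = (2/3)c².
- c = 0.2: λ = 275 × 0.02667 = 7.33; the F rejects 67.5% of the time.
- c = 0.3: λ = 275 × 0.06 = 16.5; the F rejects 96.1% of the time.

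An A-versus-B contrast rejects 5% in both cases, its nominal level. A simulation of 8,000 runs at c = 0.2 agreed: F 68.3%, contrast 5.1% with or without covariates.

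*A and B differ by 0.24 SD.* The unadjusted contrast, using the error pooled over three arms, has 80.3% power wherever C lies. The F depends on C:
- C midway: λ = 7.92, power 71.1%.
- C equal to the lower arm: λ = 10.56, power 83.6%.
- C 0.08 SD below the lower arm: λ = 15.25, power 94.7%.

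So the contrast is not always the more powerful test. Its merit is that it answers the A-versus-B question.

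**The case against.** **Nothing is wrong with the unadjusted analysis.** This stands. A reader might infer that omitting covariates biases the secondary results, since the plan cites baseline bias as its reason for adjusting the primary analyses. The documents do not support that: the comparison is randomised, and the secondary ratings have no pre-message value. Leaving them unadjusted is coherent.

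**The gain is assumed, not shown.** This also stands. Neither d nor r is in the documents, and nothing there says that cigarettes per day or motivation predicts ratings of informativeness or reactance. The case is only that a possible gain comes at almost no cost.

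**The contrast point may be empty.** The Background says the project evaluates two message packages, and comparing messages with each other reads naturally as A against B. On that reading the F is already the right test. But the plan also calls C a message, and the limit to arms A and B is not attached to these three outcomes, so three levels remain possible. A reader might infer that the plan has committed to an uninterpretable three-arm test; it has not.

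**Extra tests and timing.** The plan's false discovery rate correction covers emotionality analyses only, so added comparisons would be uncorrected. This is met by keeping one A-versus-B test per outcome and treating the unadjusted result as a sensitivity analysis. IRB approval is dated 2/15/2023 and the document 9/6/2024; whether data were already in hand is not stated. If they were, the covariates could not be called pre-specified.

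**Emotionality.** A reader might also see a contradiction between "Analyses of emotionality will use ANOVAs" and "covariate-corrected analyses involving emotionality". The second can describe analyses additional to the first, so no contradiction is shown and nothing here rests on it.

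**Conclusion.** The point holds as an optional improvement of low severity. The planned ANOVAs are valid; they leave available precision unused and do not fix their target comparison.

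The precision gain at an assumed d of 0.24 runs from nothing (r = 0) to about 2 points (r = 0.2), 4 points (r = 0.3) and 10 points (r = 0.5). Whether it is worth having depends on an r that the documents do not give.

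The contrast matters only if the water-advertisement arm is in the model. In that case a significant F is not evidence that A differs from B: it would occur 68% of the time with A equal to B and C 0.2 SD away. If only A and B are analysed, this part falls away.

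**What to change.** In the Statistical Analysis Plan:

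1. State that the secondary comparison for perceived effectiveness, reactance and informativeness is A versus B, and say whether C is in the model. If it is, specify A versus B as a planned contrast from that model.
2. Estimate the difference by ANCOVA with two named covariates, baseline motivation to quit and cigarettes per day. Both are in the survey's pre-message section. Baseline intention to quit is a less safe choice: the plan adjusts for it in the primary analyses, but Study Procedures does not list it among the baseline items.
3. Keep the unadjusted ANOVA as a sensitivity analysis.

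The cost is a few sentences, with no new data or participants. The downsides are two degrees of freedom, little gain if the correlation is weak, and a contrast that can have less power than the three-arm F when C lies at or below the lower arm. If data have already been examined, label the adjusted analysis as added afterwards.
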